### **1. Purpose of the study –**

The purpose of this study is to compare the clinical outcome of arthroscopic rotator cuff repair with and without augmentation with MSCs. Important secondary endpoints include the incidence of persistent structural defects in the tendon following surgery and the incidence of post-operative stiffness.

### **2. Background & significance –**

Mesenchymal stem cells (MSCs) have the potential to differentiate into a variety of adult cells and to provide a source of growth factors for tissue regeneration. They have been used to augment several orthopedic surgical procedures, including rotator cuff repair. Specifically, biologic augmentation of rotator cuff repair with MSCs has been shown to improve healing outcomes compared to standard rotator cuff repair. Furthermore, studies have shown that MSCs used in rotator cuff repair improve tendon integrity, which decreases the likelihood of re-tear that may occur as a result of normal rotator cuff tendon degeneration over time. In addition, stem cells may provide a more favorable biologic environment for recreation of a more normal tendon-bone interface following tendon repair. Ideally, their use can potentially reduce the risk of re-injury or improve muscle function that has been compromised following tendon disruption. The hypothesis is that there will be improved clinical outcomes and reduced incidence of recurrent structural defects in patients undergoing repair with MSCs as compared to the control group.

### **3. Design & procedures –**

This research project will evaluate the efficacy of biologic augmentation of arthroscopic rotator cuff repair with bone marrow-derived mesenchymal stem cells (MSCs) as measured by validated patient reported outcome measures. This study will be conducted as a prospective, randomized trial of 130 patients undergoing arthroscopic repair of full thickness rotator cuff tears with or without MSCs

The primary outcome measure will be the American Shoulder and Elbow Surgeons (ASES) score at one-year follow-up. Important secondary outcome measures include shoulder examination findings (range of motion, shoulder strength, and Rowe Score) and additional validated patient reported outcome measures (PROMs) about shoulder function, symptoms, daily activities, sports/recreation, and general health (the visual analog pain scale (VAS), Constant score, Simple Shoulder Test (SST), SANE score, and VR-12 Health Assessment). Subjects will undergo an MRI scan at 1 year post-operatively to determine the integrity of the repair with comparisons to standard of care, preoperative MRI anatomy and tear description at the time of surgery.

Title: A Prospective Randomized Trial of Biologic Augmentation with Mesenchymal Stem Cells in Patients Undergoing Arthroscopic Rotator Cuff Repair.

PI: [name], MBA

Secondary endpoints will include structural integrity of the tendon using MRI scan, and functional outcome using objective examination findings. A relationship between use of MSCs, pain, and stiffness may be determined as well.

#### **4. Selection of Subjects –**

Patients ages 18-70 who are determined by medical chart review and confirmed by standard of care procedures to have a full thickness rotator cuff tear and elect to have surgery will be invited to participate in this study. Potential subjects will have to meet all of the inclusion criterion and none of the exclusion criterion to participate in the study. Once a patient has met the pre-operative criteria, s/he will be offered the opportunity to participate in this study.

#### **Eligibility**

##### *Inclusion Criteria*

- Patients ages 18-70
- Patient is determined to have a full thickness rotator cuff tear (1-3 cm) or partial tear converted to a full-thickness tear—on the standard of care, pre-operative MRI scan or found arthroscopically—and is scheduled to undergo surgical repair. Pre-operative MRI data is solely abstracted from the chart.
- Written informed consent is obtained

##### *Exclusion Criteria*

- Revision surgery
- Irreparable tear or partial repair
- Any patient lacking decisional capability
- Subscapularis involvement
- Diagnosed musculoskeletal cancer or any diagnosed cancer, other than musculoskeletal if not on long term remission (e.g. at least 5 years or negative biopsy at last exam), except basal cell carcinoma
- Patients who are at higher risk for post-surgical bleeding (e.g., bleeding disorder; taking anticoagulants except low dose aspirin) or post-surgical infection (e.g., taking immunosuppressants; have a severe infection or a history of serious infection or use of systemic steroids)
- Known history of HIV, or has active Hepatitis B or active Hepatitis C
- Alcohol and drug (medication) abuse
- Pregnant or breast feeding women. Females of childbearing potential must agree to use an acceptable birth control method during study participation.
- Patients that have received PRP, other platelet-based product, or investigational treatment in another cell/biologic study for the target shoulder in the 12 months prior to the injection procedure
- Any clinically significant finding that would place the patient at health risk, impact the study, or affect the completion of the study

**Title: A Prospective Randomized Trial of Biologic Augmentation with Mesenchymal Stem Cells in Patients Undergoing Arthroscopic Rotator Cuff Repair.**

**PI: [name], MBA**

- Any psychiatric illness that would prevent comprehension of the details and nature of the study and interfere with follow-up clinic visits
- Contraindications to MR imaging

**5. Subject recruitment and compensation –**

Patients age 18-70 who are determined by medical chart review and confirmed by standard of care procedures to have a full thickness rotator cuff tear and elect to have surgery will be invited to participate in this study. Potential subjects will have to meet all of the inclusion criterion and none of the exclusion criterion to participate in the study.

Subject will not be compensated for their participation in this study.

**6. Consent process –**

The patient must be made fully aware of the protocol requirements and s/he must acknowledge his/her understanding and agreement prior to signing the informed consent. Informed consent will be obtained pre-operatively in the office setting or with an econsent through potential subject email via Rush approved, secured electronic platform, Patient IQ. Only patients recommended to undergo full thickness rotator cuff surgery by the treating surgeon will be offered enrollment in the study. Once patients are enrolled, randomization will occur prior to surgery.

The enrollment period will be ongoing until 130 patients are enrolled and all patients will be tracked for 1 year. Follow-up will take place at 7-10 days, 1 month, 6 months, and 12 months. PROMs will be obtained annually for 5 years.

**7. Study Interventions –**

**Timeline of Events**

1. Prior to signing the consent, all patients will have obtained a pre-operative MRI and standardized outlet view radiograph of their shoulder as part of their customary evaluation. Pre-operative shoulder exam will be performed, PROMs, and baseline data obtained. Pre-operative data regarding Goutalier staging will be recorded. Pre-operative MRI and shoulder exam data will solely be abstracted from charts. Pre-operative MRI and shoulder exams are not performed for research purposes.
2. Once informed consent is obtained, the patient will be randomized prior to surgery to either the MSC or non-MSC group.
3. Using clinically accepted methods, bone marrow aspiration (from hip, proximal humerus or tibia) will be performed through a small incision prior to arthroscopy in the group undergoing MSC augmentation. A small incision will be made on patients who are not undergoing MSC augmentation in order to maintain patient blinding.

Title: A Prospective Randomized Trial of Biologic Augmentation with Mesenchymal Stem Cells in Patients Undergoing Arthroscopic Rotator Cuff Repair.

PI: [name], MBA

4. Patient will undergo full thickness rotator cuff repair using a double row, TOE anchor/suture technique. Acromioplasty will be performed in all patients. Alternate procedures such as biceps tenotomy/tenodesis, distal clavicle excision will be performed at the discretion of the surgeon and recorded.
5. Intra-operative data, including size of tear, degree of retraction, and tendon quality, will be obtained during surgery.
6. MSC injection or no MSC injection will be performed according to randomization.
  - a. For MSC patients, a total of 6 mL of BMAC will be injected: 3 mL in the tendon at the junction between the bone and tendon; 3 mL in the bone at the site of the footprint
7. Identical rehabilitation using a standard accelerated protocol will be employed.
8. Subjects will return to the office for a follow-up visit at 6 weeks after surgery. VAS, SANE score and passive range of motion will be measured.
9. Subjects will return to the office for a follow-up visit at 6 months after surgery. PROMs and shoulder examination will be obtained.
10. Subjects will return to the office for a follow-up visit at 12 months after surgery. PROMs, shoulder examination and MRI will be obtained.
11. PROMs will be collected annually for 5 years.

	Pre-op	Rotator Cuff Surgery	7-10 days FU	1 mo. FU	6 mo. FU	12 mo. FU	24 mo. FU	48 mo. FU	60 mo. FU
PROMs	X		X (VAS only)	X	X	X	X	X	X
Shoulder examination			X	X	X	X			
Outlet view radiograph	X								
Intra-operative data collection		X							
MRI of shoulder						X			
Informed Consent	X								

Study Flow Sheet

Title: A Prospective Randomized Trial of Biologic Augmentation with Mesenchymal Stem Cells in Patients Undergoing Arthroscopic Rotator Cuff Repair.

PI: [name], MBA

#### Bone Marrow Concentrate Preparation

MSC injection (BMAC) will be prepared from the aspirated bone marrow using the Arthrex Angel System (Arthrex, Naples, FL). This automated centrifuge system rapidly concentrates cellular contents and growth factors in bone marrow aspirate using flow cytometry.

#### **8. Risk/benefit assessment –**

There is no direct benefit to the patient for their participation in this study. The results will contribute to the improvement in treatment of full thickness rotator cuff tears in future patients undergoing arthroscopic repair. The study will help determine whether the use of MSCs is needed in these patients with regard to functional outcome and pain relief.

Additionally, the study may help conclude whether the use of MSCs is associated with increased pain and stiffness following surgery.

#### **Alternatives to Participation**

The alternative to participation in this study is not to participate. Patients who decline to participate will be offered to proceed with the recommended rotator cuff repair, which is the current standard of care. They will return to the office for postoperative follow-up per the rehab protocol for the specific procedure performed.

#### **9. Costs to the subject**

There are no additional costs that will be incurred by subjects involved in this study.

All standard of care procedures and costs will be billed to patient insurance.

#### **10. Data Analysis and Statistical Considerations –**

A power analysis was conducted based on previously published data by MacDonald *et al.* They reported ASES scores at 2-year follow-up between patients undergoing rotator cuff repair with and without acromioplasty and found a 95% confidence interval of -13.0 to 3.2 for the score difference. Using the reported standard deviation from these 2 study groups, 10 a minimal clinically important difference (MCID) of 10 points in the ASES score, and group size of 45 patients each, we would be powered at 81.1% to detect a difference. Due to several reasons, we have had to increase our enrollment number from 100 to 130 participants. We have set a new enrollment goal of 65 patients in each of the groups for the current investigation to account for attrition.

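### Section 10 names no primary analysis model and gives pre-operative PROMs no role; prespecify ANCOVA on pre-operative ASES, if collected, with a rule for missing baselines

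*Combined protocol and SAP*

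**What the plan says.** Section 3 sets the endpoint: "The primary outcome measure will be the American Shoulder and Elbow Surgeons (ASES) score at one-year follow-up". It does not say how the arms will be compared.

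Section 10 is the only statistical text. It takes its planning values from a published trial, of which it says: "They reported ASES scores at 2-year follow-up between patients undergoing rotator cuff repair with and without acromioplasty". With a 10-point difference and that trial's SD (no figure is given), it states: "group size of 45 patients each, we would be powered at 81.1% to detect a difference". It then reports the larger target ("we have had to increase our enrollment number from 100 to 130 participants") and the reason for it ("We have set a new enrollment goal of 65 patients in each of the groups for the current investigation to account for attrition"). It names no test, model, effect measure, covariate, alpha or missing-data rule.

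Baseline data are planned. Step 1 of the Section 7 timeline says "Pre-operative shoulder exam will be performed, PROMs, and baseline data obtained", and the flow sheet marks PROMs at the pre-operative visit. No section says what these values are for.

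Pre-operative ASES is implied rather than named. Section 3 describes the other instruments as "additional validated patient reported outcome measures (PROMs) about shoulder function", which makes ASES one of the PROMs. But the set varies by visit: the flow sheet limits the 7-10 day entry to the pain scale, and step 8 of the timeline says of the 6-week visit "VAS, SANE score and passive range of motion will be measured".

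**The concern.** Two things follow from the silence in Section 10.

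- **The primary estimate is not fixed.** A comparison of 12-month scores, a comparison of change scores and a baseline-adjusted comparison all fit the present text. Each is valid if chosen in advance. Choosing among them after seeing results by arm is not, and nothing in the plan prevents it.
- **Precision may be given away.** The power statement is a plain two-group comparison with no credit for baseline. With equal arms and the same patients analysed, ANCOVA on the baseline score is asymptotically no less precise than the unadjusted comparison, and it gains whenever baseline and outcome are correlated.

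The second point has a condition. Software usually drops patients with a missing covariate, so an adjusted model with no rule for missing baselines can be less precise than the unadjusted one.

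**Working it through.** **Inputs from Section 10:** difference 10 points; 45 per arm in the power statement; 65 per arm enrolled; stated power 81.1%.

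**Assumed, because the documents give no value:** two-sided alpha 0.05 (one-sided shown at the end); r from 0 to 0.5; 5 of 45 per arm without a baseline, as an illustration.

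**1. The plan's own figure.** The 81.1% cannot be reproduced independently, since SD, alpha and sidedness are missing. It can only be solved for the SD. With noncentrality 10 / (SD × √(2/45)) and 88 degrees of freedom, power of 0.811 gives SD = 16.51. The stray 10 printed beside the mention of the SD is not that SD: it would give 99.7% power.

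**2. ANCOVA, all patients kept.** Residual SD = 16.51 × √(1 − r²), degrees of freedom 2n − 3. For example, at r = 0.3 the residual SD is 16.51 × √0.91 = 15.75.

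| Analysis | Power, 45 per arm | Power, 65 per arm |
|---|---|---|
| Unadjusted | 81.10% | 92.88% |
| ANCOVA, r = 0 | 81.09% | 92.88% |
| ANCOVA, r = 0.1 | 81.47% | 93.11% |
| ANCOVA, r = 0.2 | 82.63% | 93.79% |
| ANCOVA, r = 0.3 | 84.58% | 94.87% |
| ANCOVA, r = 0.4 | 87.29% | 96.24% |
| ANCOVA, r = 0.5 | 90.67% | 97.71% |

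The 95% CI half-width is t(0.975, df) × residual SD × √(2/n). At 45 per arm it is 6.92 points unadjusted, 6.60 at r = 0.3 and 5.99 at r = 0.5. At 65 per arm the values are 5.73, 5.47 and 4.96.

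**3. Change score, for comparison.** If the SD is the same at both times, the SD of change is 16.51 × √(2(1 − r)). Power at 45 per arm is 61.3% (r = 0.2), 67.1% (0.3), 73.7% (0.4) and 81.1% (0.5). It is below the planning figure whenever r is under 0.5.

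**4. Missing baselines (5 of 45 per arm).**

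- *Dropped, leaving 40 per arm:* ANCOVA power is 77.9% (r = 0.2), 80.1% (0.3) and 87.1% (0.5). To match 81.1%, ANCOVA needs 43.3 per arm at r = 0.2, 41.1 at 0.3 and 34.0 at 0.5.
- *Kept, with the pooled mean imputed:* if baselines are missing at random, residual SD = 16.51 × √(1 − r² × 40/45). At r = 0.3 that is 16.51 × √0.92 = 15.84. With 87 degrees of freedom, power is 82.5% (r = 0.2), 84.2% (0.3) and 89.7% (0.5). Simulation with 8,000 trials per setting gave 82.2%, 84.0% and 89.6%, and a type I error of 4.9% at r = 0.3.

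**5. One-sided alpha 0.05 instead.** The implied SD is 18.63. ANCOVA power at 45 per arm is 84.2% (r = 0.3) and 89.8% (r = 0.5), so the pattern is similar.

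**The case against.** The strongest reply is that only the missing model is a defect. A named two-sample comparison of 12-month scores would cure it, and ANCOVA is then a preference whose benefit depends on an r that the documents do not give. At r = 0.2 the gain is 1.5 points of power at 45 per arm (82.6 − 81.1) and 0.9 at 65 (93.8 − 92.9). Nothing in the documents suggests that baselines will be missing. Nor would the proposed wording fix everything: the analysis population and missing 12-month scores stay open, and enrolling 130 against 90 in the power statement allows 1 − 90/130 = 30.8% loss.

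Most of this is fair. Any named model would fix the estimate, the size of the gain is assumed, and the missing-baseline figure is illustrative. The open questions on analysis population and missing outcomes are real, but they call for further text and do not count against this change. ANCOVA remains the better model to name because its downside is one degree of freedom (81.10% to 81.09% at r = 0), and the missing-baseline rule keeps it from losing patients.

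It can also be said that the pre-operative PROM entry carries no restriction, so ASES is naturally included. That is the likely reading. It still needs confirming, because a pre-operative score that was not collected cannot be recovered.

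**Conclusion.** The concern holds and should be acted on. No primary model is named, and the scheduled baseline PROMs have no analysis role. This does not make an unadjusted analysis biased, and it does not show that 81.1% is wrong.

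Given the back-solved SD of 16.5 and two-sided 0.05, ANCOVA at 45 per arm adds between nothing (r = 0) and 9.6 points of power (r = 0.5: 90.7 − 81.1). The gain is modest at r of 0.2 or less and sizeable only from about 0.4. It depends on pre-operative ASES being collected and on patients without it being kept. The benefit of fixing the model in advance does not depend on r.

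**What to change.** Add to Section 10, before any outcome is examined by arm:

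> The primary analysis is a linear model (ANCOVA) of 12-month ASES on randomised arm with pre-operative ASES as covariate, two-sided alpha 0.05, reporting the adjusted mean difference and 95% CI. Patients missing pre-operative ASES are kept, with the covariate set to the overall mean of the observed pre-operative values, pooled across arms.

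Also:

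- Name ASES among the pre-operative PROMs in Section 7, step 1, and in the flow sheet. Confirm that it has been collected from any patients already enrolled.
- Analyse continuous secondary PROMs the same way where a baseline value exists.
- Describe 81.1% as the unadjusted planning figure, and state its SD, alpha and sidedness.

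The cost is a short addition to Section 10, small edits to Section 7 and the flow sheet, a check of data already held, and one degree of freedom. No more patients are needed. No new data are needed if pre-operative ASES is already collected. The analysis population and the handling of missing 12-month scores need their own text.

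### Section 10 meets attrition only by enrolling more patients and states no use of pre-operative or 6-month ASES, which could add precision and could reduce bias from selective loss

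*Combined protocol and SAP*

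**What the plan says.** Section 3 sets the endpoint: "The primary outcome measure will be the American Shoulder and Elbow Surgeons (ASES) score at one-year follow-up".

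Section 10 contains a power statement and enrolment targets. With a 10-point difference and "group size of 45 patients each, we would be powered at 81.1% to detect a difference", it goes on to say that "we have had to increase our enrollment number from 100 to 130 participants", and then: "We have set a new enrollment goal of 65 patients in each of the groups for the current investigation to account for attrition". It prints no SD or alpha. It names no primary model, covariate or method for missing scores, and no other section supplies them.

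The eligibility criteria try to limit loss in advance, for example by excluding "Any clinically significant finding that would place the patient at health risk, impact the study, or affect the completion of the study". That is prevention; it does not say how missing scores are analysed.

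Section 7 (Timeline of Events, steps 1, 9 and 10) and the Study Flow Sheet schedule PROMs before surgery and at 6 and 12 months. ASES is not named at each visit. It is inferred to be included because Section 3 assesses efficacy "as measured by validated patient reported outcome measures", makes ASES primary, and calls the other scores "additional validated patient reported outcome measures (PROMs) about shoulder function". The sponsor should confirm this.

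**The concern.** Extra enrolment restores the number of completers. It does not make the completers representative. If patients doing poorly at 6 months are more likely to miss the 12-month visit, and this works differently in the two arms or the arms lose different proportions, a comparison of completers is biased at any sample size. The 6-month score carries information about those patients, and the trial already plans to collect it.

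There is also a possible loss of precision. The power statement contains no covariate, so it reads as a plain two-group comparison. A baseline score correlated with the outcome would narrow the confidence interval without another patient. With no stated method, the choice between a completer comparison and a model using earlier scores could be made after the data are seen.

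**Working it through.** **Inputs from Section 10.** 45 per group for power, 65 per group enrolled, 10-point difference, 81.1% power, earlier total 100.

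**Assumptions, not in the documents.** Two-sided 5% alpha; correlation of baseline with 12-month ASES r = 0.1 to 0.5; baseline with 6-month correlation r + 0.1; 6- with 12-month correlation 0.65; the loss rates and dropout odds ratios below.

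**1. The plan's own figure.** The SD is not printed, so 81.1% cannot be checked independently. Solving the two-sample t-test for 81.1% power at 45 per group gives SD 16.51 (18.63 if one-sided 5%). At SD 16.51, 65 per group with no loss gives 92.9%.

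**2. Tolerance for loss.** 1 − 45/65 = 30.8%. The earlier 50 per group gave 1 − 45/50 = 10%.

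**3. Precision under random loss.** Simulated standard errors, 65 per group; the last column assumes every lost patient has a 6-month score:

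| r | Loss | Unadjusted | Baseline-adjusted | Baseline + 6-month |
|---|---|---|---|---|
| 0.2 | 10% | 3.08 | 3.02 | 2.96 |
| 0.2 | 31% | 3.50 | 3.45 | 3.25 |
| 0.4 | 10% | 3.06 | 2.83 | 2.77 |
| 0.4 | 31% | 3.52 | 3.26 | 3.11 |

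Large-sample check. The baseline cut is 1 − √(1 − r²): 2.0% at r = 0.2, 8.3% at 0.4, 13.4% at 0.5. The further cut from the 6-month score is 1 − √(1 − p²L), where L is the loss rate and p the partial correlation of 6- and 12-month scores given baseline.

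- r = 0.2: p = (0.65 − 0.2×0.3)/√(0.96×0.91) = 0.631. The further cut is 2.0% at L = 0.10 and 6.3% at L = 0.308.
- r = 0.4: p = (0.65 − 0.4×0.5)/√(0.84×0.75) = 0.567. The further cut is 1.6% and 5.1%.
- r = 0.5: p = (0.65 − 0.5×0.6)/√(0.75×0.64) = 0.505. The further cut at L = 0.308 is 4.0%.

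In finite samples the baseline cut is about 0% (r = 0.1), 1–2% (0.2), 4–5% (0.3), 7–8% (0.4) and 11–13% (0.5). At zero loss the 6-month score adds nothing. Power for 10 points at 31% loss, in the order of the table columns, is about 81 / 82 / 86% at r = 0.2 and 81 / 86 / 89% at r = 0.4. At 10% loss it is 90 / 91 / 92% and 90 / 94 / 95%.

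**4. Bias of unadjusted completers.** No true effect; a lower 6-month ASES makes loss more likely; equal loss rates in the two arms; r = 0.4 (r = 0.2 is similar). Odds ratios are per SD of 6-month ASES:

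| Selection | 10% loss | 31% loss |
|---|---|---|
| Same in both arms | 0 | 0 |
| Odds ratio 2 against 3 | 0.3 | 0.9 |
| 2 in one arm, random in the other | 0.7 | 2.1 |
| 3 in one arm, random in the other (extreme) | 1.0 | 3.0 |

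Check: the bias is SD × 0.65 × the between-arm difference in completers' mean standardised 6-month score. Since 16.51 × 0.65 = 10.73, a 3.0-point bias needs a difference of 3.0/10.73 = 0.28 SD.

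Type I error is P(|Z + bias/SE| > 1.96): 5.1–6.3% at 10% loss and 5.8–13.8% at 31%.

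Unequal rates (21% against 41%): 0 if loss is random. With an odds ratio of 2 in both arms the bias is 1.3 points unadjusted, 0.9 baseline-adjusted and 0.0 with the 6-month score.

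**5. Limits of the remedy.** In the extreme case at 31% loss and r = 0.4, the bias after modelling is 0 if all lost patients have a 6-month ASES, 0.8 if half do and 2.1 if none do. If one arm's loss depends on the unseen 12-month score itself (odds ratio e ≈ 2.7 per SD, 31% loss, 6- to 12-month correlation 0.5 to 0.7), the completer bias of about 4.4 points falls only to 3.4–2.4.

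**The case against.** The strongest reply is that every size here is assumed. The documents give no correlation, SD, loss rate or dropout pattern. That stands, and it is why the point says these scores could help. A reader might infer that they would certainly raise precision; at r = 0.1 and low loss the gain is close to nil.

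A reader might also take 31% as the loss the sponsor expects, or conclude that the trial is underpowered. Neither follows. The figure is a tolerance, and within it the stated power holds for a completer analysis under random loss. Biases of 2 to 3 points need loss near that tolerance together with selection in one arm only. Section 7 (step 3) plans an incision in the control arm to keep patients blinded, which makes arm-specific loss less likely without excluding it.

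Nor does a difference in loss rate alone cause bias; the rate matters only when loss also depends on scores. The bias table assumes no true effect. With a 10-point effect and the same selection in both arms, completers gave about −0.5 points, a small error.

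It can fairly be said that the wider gap is the absence of any named primary analysis, and that the mixed model is one of several sound choices; multiple imputation with the same variables would serve. PROMs from later years could also inform a missing 12-month score if the analysis waited for them.

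Finally, a reader might charge patients found at surgery to meet an exclusion such as "Irreparable tear or partial repair" against the 20 spare places. The documents do not say that such patients are removed and give no number, so that is not part of this point.

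**Conclusion.** The point holds as a cheap improvement to the plan. It does not show that the result will be biased or imprecise. Attrition is met in Section 10 only by 65 against 45 per group, and no use of earlier ASES scores is stated.

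The likely precision gain runs from nothing to useful, and it depends mainly on the baseline correlation. The 6-month score does little for precision at 10% loss and more near the tolerance. Its main value is against bias: baseline adjustment alone left 0.9 of 1.3 points in the unequal-rate case, while adding the 6-month score removed it.

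These results assume SD 16.5 (biases scale by 1.13 at SD 18.63; percentage cuts in the standard error do not change), the stated correlations, missing-at-random given baseline and 6-month ASES, and a 6-month score for the patients lost. Against the 10-point target, the biases at stake are small at 10% loss and reach 3 points only in the extreme case at 31%.

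**What to change.** In Section 10, state the primary analysis as the 12-month difference between arms in ASES, with patients in their assigned arm, adjusted for baseline ASES and using 6-month ASES. A mixed model for repeated measures would do this (baseline ASES, arm, visit, baseline-by-visit, arm-by-visit, unstructured covariance), as would equivalent multiple imputation. Add one delta-adjusted sensitivity analysis to probe the missing-at-random assumption; it also covers patients with neither a 6- nor a 12-month score. Confirm in the visit schedule that ASES is collected before surgery and at 6 months.

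Do not bring the early post-operative visit into the model yet. Section 6 and the Study Flow Sheet place it at 1 month, the flow sheet with PROMs, while Section 7 (step 8) describes a 6-week visit with VAS, SANE and passive motion. These must be reconciled first.

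The cost is a few sentences and slightly more analysis work, with no new visits or data. The downside is reliance on missing-at-random. If baseline correlation and loss are both low (r about 0.2 or less, 10% loss), the gain in precision is only about 2–4%.
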